6.1.2.2 DLT Evaluation Period

From treatment initiation until Day 28 in Part A.

6.1.2.3 DLT Evaluable Subjects

Subjects meeting any of the following criteria enrolled in a cohort in Part A.

- Subjects who have taken at least 80% of the doses of TAK-385 (23 doses) during the DLT evaluation period and for whom the DLT evaluation period observations have been completed.
- Subjects who experienced DLTs during the DLT evaluation period.

## 6.2 Rationale for Study Design, Dosage, and Endpoints

(1) Rationale for the target patient population and the study design

The novel GnRH antagonist TAK-385 is expected to compensate for the deficiencies of the GnRH agonists that have been widely used in the treatment of prostate cancer to date, and is being developed as a novel therapeutic medication for prostate cancer. The target patient population for this study was therefore made Japanese patients with prostate cancer.

Because this study will be the first time in Japan that TAK-385 will be administered to patients with prostate cancer, and the safety and efficacy of TAK-385 for the target population have not been sufficiently demonstrated, the TAK-385 treatment period in Part A was set at 28 days. The treatment period would minimize the

inconvenience to subjects with safety concerns or insufficient efficacy. Because TAK-385 will be administered alone to hormone treatment-naive patients with prostate cancer, a placebo would not be used, and that the study would be conducted as an open-label study. It was also decided that if a subject is going to be switched to some other therapy after receiving the last dose of TAK-385 in Part A, then the patient would have to first pass through a 1-week observation (no-treatment) period because of concerns about the safety of the temporary concomitant use of TAK-385 with other therapies. However, subjects meeting the discontinuation criteria (Section 7.5) during the 28-day treatment period would not need to first pass through a 1-week observation period if they need to be switched to some other therapy immediately.

The treatment period in Part B was made 48 weeks long in order to investigate safety and efficacy over a longer period, in light of the fact that the safety and efficacy of TAK-385 in multiple dosing for 28 days will have been confirmed in Part A. If the investigator or sub-investigator determines after 48 weeks that there are no safety problems and that TAK-385 treatment may be continued, then treatment may be continued for up to a total of 96 weeks. Part B was made an open-label phase with randomization to one of two doses the tolerability of which will have been confirmed in Part A. An open-label study design was used because TAK-385 is being administered alone to hormone treatment-naive patient with prostate cancer. In addition, if a subject is going to be switched to some other treatment after the last dose of TAK-385 then, unlike in Part A, and assuming use in the actual clinical setting, it was decided that the other therapy could be initiated without any intervening observation period for confirming the safety of temporary concomitant use with the other therapy.

Furthermore, TAK-385 has been found to be affected by food, and the results that have been obtained suggest that TAK-385 absorption is decreased and delayed when a single dose is taken 30 minutes after food compared to when it is taken in a fasted condition (TAK-385\_C27001). It was therefore decided that TAK-385 should be taken at least 30 minutes before breakfast.

Because the company plans to participate in multinational studies in the future, it was decided that Part B would be conducted using the same dosage and administration as that being used in the phase 2 studies being conducted overseas. Because Part B will be conducted using a dosage the tolerability of which will have been confirmed in Cohorts 1 and 2 in Part A, it was decided that Part A Cohort 3 and Part B could be conducted in parallel.

(2) Rationale for loading dose (Part A, Cohort 1)

In a phase 1 study in healthy adult males that was conducted in Europe (TAK-385\_C27001), the tolerability of single doses as high as 360 mg and multiple doses as high as 160 mg was confirmed. In order to keep serum testosterone at castration levels and maintain this effect, it was felt that a dose of at least TAK-385 80 mg a day would be necessary as a maintenance dose. In addition, in study

TAK-385\_C27001, single doses of TAK-385 180 mg and above reduced serum testosterone levels to castration levels within 48 hours.

Based on these existing data on TAK-385 and on the development plan, it was decided that the loading dose for Cohort 1 in Part A of this study should be 320 mg, a dose that is within the range of doses that have been confirmed to be safe in single dosing, and that can be reliably expected to suppress serum testosterone levels within 48 hours. Given that TAK-385 is going to be used in patients with prostate cancer, the company concluded that it would be necessary to use a dose that could be expected to be effective from the beginning, and that this dose would be tolerated as the loading dose in Japanese. The maintenance dose was set at 80 mg, which can be expected to suppress serum testosterone levels.

(3) Rationale for dosage in Part A, Cohort 4

320 mg or 360 mg may be selected as the loading dose in the planned phase 3 multinational study. Based on this situation, a new cohort, Cohort 4, was added to Part A in Amendment 2 of the study protocol, designed to evaluate the tolerability of loading dose of 360 mg in Japanese patients before joining the phase 3 multinational study. As for the maintenance dose, the same dose as Part A, Cohort 2 (120 mg) was selected, since this dose is expected to keep serum testosterone at castration levels and maintain this effect.

As described in the section above, the tolerability of single doses of 360 mg and multiple doses as high as 160 mg (for 28 days) has been confirmed in a phase 1 study in healthy adult males that was conducted in Europe (TAK-385 C27001).

 Based on the fact that there are no major differences between Japanese and Americans in the pharmacokinetic or pharmacodynamic profiles of TAK-385, and that there are no major differences between the pharmacokinetic profiles obtained in healthy adult men and women, there are no safety concerns in using the loading dose of 360 mg and maintenance dose of 120 mg in Part A, Cohort 4.

(4) Rationale for endpoints

1) Rationale for the primary endpoints

The endpoint in Part A is DLT, in order to confirm the tolerability of TAK-385 in multiple dosing. AEs, clinical laboratory tests, vital signs, and 12-lead ECGs were also made primary endpoints, in order to confirm safety.

In part B, the primary endpoints were made AEs, clinical laboratory tests, vital signs, and 12-lead ECGs, in order to confirm the safety of the use of TAK-385 in multiple dosing for 48 weeks.

## 2) Rationale for secondary endpoints

In both Part A and Part B, the plasma concentrations of unchanged TAK-385 will be investigated in order to confirm the PK of TAK-385 in multiple dosing. The change in serum testosterone levels over time will also be investigated, in order to confirm the pharmacodynamics. In addition, in Part B, PSA levels will also be evaluated in order to investigate the efficacy of TAK-385 in prostate cancer.

## 3) Rationale for other endpoints

In Part A, the changes over time in the blood levels of LH, FSH, DHT, and SHBG, which are involved in testosterone synthesis, will be investigated. PSA levels will also be evaluated, in order to preliminarily investigate the efficacy of TAK-385 in prostate cancer.

In Part B, disease progression assessed on the basis of PSA and disease progression assessed on the basis of imaging assessments will be evaluated in accordance with the Prostate Cancer Handling Guidelines, Fourth Edition [16], in order to preliminarily investigate the efficacy of TAK-385 in prostate cancer. In addition, as in Part A, the changes over time in the blood levels of LH, FSH, DHT, and SHBG will also be investigated. Moreover, because androgen-deprivation therapy is known to promote loss of bone mineral density and increase the potential for bone fractures, bone density tests were specified in order to evaluate the effects of TAK-385 on bone mineral density. In nonclinical studies, changes suggesting systemic phospholipidosis have been found in the organs/tissues of animals. Therefore, in order to closely monitor subjects for phospholipidosis, ophthalmology tests were specified, as was assessment of the level of di-docosahexaenoyl (22:6)-bis(monoacylglycero)phosphate (BMP) [14, 15]. Furthermore, in order to evaluate the effects of TAK-385 on quality of life in patients with prostate cancer, quality of life assessments will be performed using the Japanese versions of AMS, EORTC-QLQ-C30, and EPIC, which are widely used in clinical studies overseas.

## 6.3 Premature Termination or Suspension of Study or Investigational Site

### 6.3.1 Criteria for Premature Termination or Suspension of the Study

The study will be completed as planned unless one or more of the following criteria are satisfied that require temporary suspension or early termination of the study.

- New information or other evaluation regarding the safety or efficacy of the study drug that indicates a change in the known risk/benefit profile for the product, such that the risk/benefit is no longer acceptable for subjects participating in the study.
- The SMC recommends that the study be suspended or terminated.
- Significant violation of GCP that compromises the ability to achieve the primary study objectives or compromises subject safety.

### **6.3.2 Criteria for Premature Termination or Suspension of Investigational Sites**

An investigational site may be terminated prematurely or suspended if the site (including the investigator) is found in significant violation of GCP, protocol, or contractual agreement, is unable to ensure adequate performance of the study, or as otherwise permitted by the contractual agreement.

### **6.3.3 Procedures for Premature Termination or Suspension of the Study or the Participation of Investigational Site(s)**

In the event that the sponsor, an institutional review board (IRB)/independent ethics committee (IEC) or regulatory authority elects to terminate or suspend the study or the participation of an investigational site, a study-specific procedure for early termination or suspension will be provided by the sponsor; the procedure will be followed by applicable investigational sites during the course of termination or study suspension.

## 7.0 SELECTION AND DISCONTINUATION/WITHDRAWAL OF SUBJECTS

All inclusion and exclusion criteria, including test results, need to be checked before study treatment initiation (Part A) or randomization (Part B).

### 7.1 Inclusion Criteria

Subject eligibility will be determined based on the following criteria.

1. Patients judged by the investigator to have the capacity to understand the study and follow the study rules.
  2. Patients whose written consent (signature or printed name and personal seal on informed consent form) can be obtained before any study procedures are performed.
  3. Japanese male patients 20 or more years of age at the time of informed consent.
  4. Patients who, if they have a female partner who could become pregnant, agree to practice appropriate means of contraception from the time of informed consent throughout the entire study treatment period and for 4 months after the last dose of study drug.
  5. Patients in stable medical condition, including the absence of acute exacerbations of chronic illnesses, serious infections, or major surgery within 4 weeks (28 days) prior to study treatment initiation.
  6. Patients with histologically or cytologically confirmed prostate cancer.
  7. Patients whose clinical diagnosis is T1-4 N0 M0, or Tx N0 M0 for patients who have undergone radical prostatectomy.
  8. Patients who are considered eligible for hormone therapy for prostate cancer.
  9. Patients who have not received hormone therapy (eg, GnRH agonist, GnRH antagonist, steroidal antiandrogen, non-steroidal androgen) for prostate cancer.
  10. Patients who have not undergone surgical castration.
  11. Patients with serum testosterone at screening > 150 ng/dL.
  12. Patients meeting either of the following criteria for PSA at screening.
    - Untreated prostate cancer: PSA at screening > 4.0 ng/mL
    - Treated\* prostate cancer: PSA at screening > 0.2 ng/mL
- \*: Patients who have undergone prostatectomy or either or both of high intensity focused ultrasound therapy or radiotherapy (excluding I-brachytherapy) prior to the start of this study.
13. Eastern Cooperative Oncology Group (ECOG) performance status [17] of 0 or 1 (Appendix G)
  14. Body mass index (BMI\*) at screening  $\geq 18.0 \text{ kg/m}^2$
- \*: BMI will be calculated by the investigational site using the following formula:  $\text{BMI} = \text{Body weight (kg)} / (\text{height (m)})^2$

Body weight will be measured in kilograms to the first decimal point, height will be measured in centimeters using integers only, and the results obtained for BMI will be rounded off to the first decimal point.

Example: Weight = 79.2 (kg), height = 176 (cm) = 1.76 (m); BMI =  $79.2/1.76^2 = 25.6$  (kg/m^2)

## 7.2 Exclusion Criteria

Patients meeting any of the following criteria will be excluded from the study.

1. Patients exhibiting symptoms judged related to prostate cancer by the investigator (eg, bone pain, pelvic pain, ureteral obstruction) who urgently require hormone therapy such as GnRH agonist, GnRH antagonist, or combined androgen blockade (CAB)/ maximum androgen blockade (MAB) therapy, chemotherapy, or radiotherapy.
2. Patients who have received 5-alpha reductase inhibitors (except for patients who have been treated for male-pattern alopecias).
3. Patients who have received chemotherapy for prostate cancer (including estramustine).
4. Patients who have received I-brachytherapy.
5. Patients who received radiotherapy (except for I-brachytherapy) within 16 weeks (112 days) before study treatment initiation.
6. Patients who underwent prostatectomy within 16 weeks (112 days) before study treatment initiation.
7. Treatment with any investigational compound within the 4 weeks (28 days) prior to the first dose of study drug or ongoing participation in another experimental trial related to the treatment of prostate cancer.
8. Diagnosis or treatment for another systemic malignancy within 2 years before study treatment initiation, or who had received a diagnosis of another malignancy before that and have evidence of residual disease. Patients with non-melanoma skin cancer or carcinoma in situ who have undergone complete resection will not be excluded from the study.
9. Patients taking drugs with moderate to strong CYP3A4 inhibitory or inducing effects, or any medications, supplements, or food products with P-gp inhibitory effects, in the 2 weeks (14 days) prior to study treatment initiation.
10. Patients who have received TAK-385 in a past clinical study.
11. Patients for whom it would be difficult to collect blood from a peripheral vein.
12. Patients with uncontrolled and clinically significant nervous, circulatory, pulmonary, hepatic, renal, metabolic, gastrointestinal, urogenital, or endocrine disorders, or other abnormalities (except for the targeted disease) that could affect study participation or the study results. Also, patients meeting any of criteria a through c below.

- a. Patients with uncontrolled diabetes (HbA1c > 8% at screening). However, patients whose HbA1c is brought under control with diabetes medications may be rescreened.
  - b. Patients with uncontrolled hypertension (systolic blood pressure > 150 mmHg and diastolic blood pressure > 90 mmHg at 2 separate measurements taken no more than 60 minutes apart at screening). Patients whose blood pressure is brought under control by antihypertensive medication may be rescreened.
  - c. Patients with myocardial infarction, unstable symptomatic ischemic heart disease, arrhythmias of CTCAE Grade > 2, thromboembolism (deep vein thrombosis, pulmonary embolism, or symptomatic cerebrovascular events), or other heart diseases (eg, pericardial effusion, restrictive cardiomyopathy). However, chronic stable atrial fibrillation controlled by stable anticoagulant therapy will be allowed.
13. Patients with bilateral hydronephrosis or bladder neck outlet obstruction.
  14. Known hypersensitivity to TAK-385, TAK-385 excipients, or GnRH antagonists.
  15. Patients with a past history of gastrointestinal tract treatments (including gastrectomy) or gastrointestinal disease that could affect the drug absorption or tolerability (malabsorption, esophageal reflux, peptic ulcer, erosive esophagitis).
  16. Patients positive for hepatitis B surface antigens (HBsAg), hepatitis C virus (HCV) antibodies, human immunodeficiency virus (HIV) antibodies, or serologic test for syphilis, or with life-threatening disease other than cancer, at screening.
  17. Clinically relevant ECG abnormalities, or the following ECG abnormalities, at screening.
    - a. Q-wave infarction, unless identified 6 or more months prior to TAK-385 treatment initiation
    - b. QTcF interval > 450 msec (when calculating the QTc interval, Fridericia's equation  $[QT/RR^{0.33}]$  will be used)
  18. Patients with congenital QT prolongation.
  19. Current use of Class 1A or Class 3 antiarrhythmic medications.
  20. New York Heart Association [18] Class III or IV heart failure ([Appendix H](#)).
  21. Patients with clinical laboratory abnormalities suggesting clinically relevant underlying disease, or with any of the following abnormal results, at screening.
    - Serum creatinine  $\geq 2.0$  mg/dL
    - ALT or AST  $\geq 1.5 \times$  ULN for the investigational site
    - Total bilirubin  $\geq 2 \times$  ULN for the investigational site
    - Neutrophil count < 1,500/mm^3, platelet count < 100,000/ $\mu$ L, hemoglobin < 10.0 g/dL

- Results of heart-related tests (creatine kinase MB [CK-MB] and cardiac troponin T) exceeding the investigational sites reference value.
- 22. Patients found to have clinical problems on the basis of examination findings, ECG findings, or chest X-ray findings at screening.
- 23. Patients considered unlikely by investigators to be able to follow the study protocol or considered ineligible for the study by investigators for other reasons.

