### **7.3 Prohibited Concomitant Medications, Therapies, and Foods**

#### **7.3.1 Prohibited Concomitant Medications**

The concomitant use of the following medications will be prohibited during the treatment period out of concern for the effects on safety, PK, and pharmacodynamics.

Furthermore, in Part A, the prohibited concomitant medications may not be used until the end of the post-treatment observation period.

- GnRH agonists
- GnRH antagonists
- Steroidal antiandrogens
- Nonsteroidal antiandrogens
- Drugs that include corticosteroids (except for topical drugs)
- Male sex hormone preparations
- Female sex hormone preparations
- 5 $\alpha$  reductase inhibitors
- Docetaxel
- Other chemotherapy drugs indicated for prostate cancer
- Drugs with moderately powerful to strongly powerful CYP3A4 inhibitory or inducing effects
- Drugs with P-gp inhibitory effects

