### 2. Study treatment

Investigators will instruct subjects to take the study drug 30 minutes before breakfast on each day, and to make sure that the time they take the study drug is the same on each day, to the extent possible.

If a subject forgets to take the study drug 30 minutes before breakfast, the subject should take the drug 30 minutes before lunch on the same day. If a subject forgets to take the study drug both 30 minutes before breakfast and 30 minutes before lunch, the subject should take the study drug 30 minutes before dinner on the same day. It will be explained to subjects that they should not take any study drug that they have forgotten to take on a later day together with the study drug for that day. Subjects will

also be instructed to be sure to note in the patient diary the time they took the study drug as well as whether or not they took the study drug 30 minutes before breakfast.

On scheduled outpatient visit days, subjects will be asked to come to the investigational site in the morning without taking the study drug, and the scheduled tests will be performed.

3. Drinks, etc.

On days on which study drug is to be taken, subjects will be prohibited from drinking anything from 1 hour before dosing until 30 minutes after, other than one cup of water when they take the study drug.

4. Other

Investigators will instruct subjects that, if a subjective symptom emerges, it should be reported, along with the date of onset, severity, outcome, and date of outcome, when the subject next visits the investigational site.

Investigators will instruct subjects not to take any drugs, including over-the-counter drugs, other than the drugs that they are instructed to take, without consulting the investigator in advance.

Subjects will be instructed that, if they are treated at another medical institution in the time between the treatment period and the safety follow-up, they are to report the background for and nature of said treatment to the investigator, and to inform the medical institution in question that they are participating in a clinical study.

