## 2. Major protocol deviation

This will be considered the primary reason for study withdrawal if it is discovered after the first dose of study treatment (in the case of Part A) or after randomization (in the case of Part B) that the subject does not meet the enrollment criteria specified in the study protocol, or has not followed the study protocol, and that continuing the study would pose an unacceptable risk to the subject's health.

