#### **9.1.16 Concomitant Medications**

The term concomitant medication refers to any drug given in addition to the study drug. These may be prescribed by a physician or obtained by the subject over the counter. At each study visit, subjects will be asked whether they have taken any medication other than the study drug (used from signing of informed consent through safety follow-up), and all medication including vitamin supplements, over-the-counter medications, and oral herbal preparations, must be recorded in the eCRF.

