### 9.3.6 Continuation Treatment Period

In Part B, if a subject continues receiving the study drug after 48 weeks, the following tests, observations, and assessments will be performed every 12, 24, or 48 weeks.

- Physical examination
- Vital signs
- Weight
- ECOG performance status
- 12-lead ECG
- Imaging assessments
- Clinical laboratory tests (hematology, chemistry, metabolic panel, and urinalysis)
- Pharmacodynamic assessments (serum testosterone, LH, FSH, DHT, and SHBG)
- Tumor marker (PSA)
- Concomitant medications
- Concomitant therapies
- AEs
- Treatment compliance
- Bone mineral density
- QOL assessments

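### Class 1A and Class 3 antiarrhythmics are excluded at entry but not prohibited on treatment, and no rule or ECG is tied to starting one

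*Protocol*

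**What the plan says.** Protocol 7.2, criterion 19, excludes "Current use of Class 1A or Class 3 antiarrhythmic medications". It follows criteria 17b (QTcF above 450 msec) and 18 (congenital QT prolongation). Section 7.0 has all entry criteria checked before treatment initiation in Part A or randomization in Part B, so criterion 19 does not operate after that.

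Section 7.3.1 is the on-treatment rule: "The concomitant use of the following medications will be prohibited during the treatment period". Safety is one of its three stated reasons. None of its 12 items names an antiarrhythmic class. Two could catch individual agents through their interaction properties: the item on moderate to strong CYP3A4 inhibitors or inducers, and "Drugs with P-gp inhibitory effects". Sections 7.3.2 and 7.3.3 cover prostate cancer therapies and foods or supplements only.

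Three other provisions bear on the point.

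- Section 7.4, item 4, tells subjects "not to take any drugs, including over-the-counter drugs, other than the drugs that they are instructed to take" unless they first consult the investigator.
- Section 9.1.16 provides for capture: "At each study visit, subjects will be asked whether they have taken any medication other than the study drug".
- Criterion 12c admits some patients with a rhythm disorder: "chronic stable atrial fibrillation controlled by stable anticoagulant therapy will be allowed".

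**The concern.** The sponsor judged these two classes unsuitable for a man about to start TAK-385, but the plan does not say whether that judgement continues once he is taking it. Section 7.4 requires consultation; it does not stop the investigator from prescribing the drug. A combination refused on Day -1 can thus be started later, in an outpatient Part B lasting 48 to 96 weeks.

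What is at stake is patient safety. The 12-lead ECG is a primary safety endpoint in Part B, yet starting one of these drugs does not itself call for an ECG or for a decision on continuing TAK-385. Because the drug is not prohibited, its use is also not a departure from the protocol to be documented under 14.2. Nor does it open the withdrawal route in 7.5, item 2, which needs a subject who fails the enrollment criteria or "has not followed the study protocol, and that continuing the study would pose an unacceptable risk".

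**Working it through.** The plan states no figure on this point, so the check compares the lists and then works through the visit schedule.

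**Drug restrictions at entry and on treatment**

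| Entry restriction (7.1, 7.2) | Counterpart in 7.3.1 |
|---|---|
| Hormone therapy (inclusion 9) | Yes |
| 5-alpha reductase inhibitors (exclusion 2) | Yes |
| Chemotherapy (exclusion 3) | Yes |
| CYP3A4 and P-gp drugs (exclusion 9) | Yes |
| Investigational compounds (exclusion 7) | No |
| Class 1A or Class 3 antiarrhythmics (exclusion 19) | No, except agents caught by the CYP3A4 or P-gp items |

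Among the restrictions on marketed drugs, only criterion 19 has no on-treatment counterpart of its own.

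**What happens if such a drug is started**

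1. If the reason is a new arrhythmia, or worsening of a permitted one, 10.1.3 would normally make it an adverse event. Sections 10.1.12 and 10.2.1.2 then require the action taken on study drug to be recorded, 7.5 item 1 provides for withdrawal at unacceptable risk, and 8.1.3.2 allows interruption. A decision on TAK-385 is prompted.
2. If the reason is a concurrent condition that has not worsened, such as stable atrial fibrillation admitted under 12c, 10.1.3 says it is not an adverse event. That route is then not triggered.
3. In neither case does the text require an ECG because the drug was started. Note c of Appendices A and B and note b of Appendix C allow additional assessments at the investigator's discretion.

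**How far apart the scheduled ECGs are**

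Inputs: Part B visits from Protocol Appendices B and C; ECG visits from SAP 6.3.2.2. Nominal day = (week - 1) × 7 + 1.

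- Visits from Week 5: Days 29, 57, 85, 113, 141, 169, 197, 225, 253, 281, 309, 337, then 421, 505, 589, 673. The spacing is 28 days up to Day 337 and 84 days after it. In the continuation period, "the following tests, observations, and assessments will be performed every 12, 24, or 48 weeks".
- ECG visits from Week 5: Weeks 5, 25, 49, 73 and 97, which are Days 29, 169, 337, 505 and 673.
- ECG gaps: 169 - 29 = 140; 337 - 169 = 168; 505 - 337 = 168; 673 - 505 = 168 days.
- Visits after Day 29: 15. With an ECG: 4. Without: 15 - 4 = 11.

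If starting the drug prompted an ECG no later than the next visit, the longest nominal wait would fall from 140 or 168 days to 28 days (Weeks 5 to 49), and from 168 to 84 days (Weeks 49 to 97).

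**The case against.** The strongest reply is that the plan already covers the cases that matter. A drug of this kind is normally given for an arrhythmia, and the adverse event rules then prompt a decision on TAK-385. The investigator is consulted beforehand, asks about medication at every visit, and may order an ECG at any time. SAP 2.2.3 tabulates concomitant drugs by class and name. This largely stands. A reader might infer that nothing in the plan prompts a decision on TAK-385; the documents do not support that. What remains is narrower: the trigger is the event and not the drug, and no ECG is required.

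Second, the number of agents affected is unknown. The P-gp item has no potency threshold, and the documents do not say which Class 1A or Class 3 drugs fall outside it. This stands and limits the size of the point.

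Third, the two lists were never copies of each other. Section 7.3.1 adds systemic corticosteroids and omits investigational compounds, and criterion 19 may partly screen for underlying heart disease. This stands as a reason not to call the difference a contradiction: criterion 19 governs entry only. It does not explain why a list justified partly by safety leaves the class out.

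Fourth, the ECG gaps describe a schedule and not harm. They ignore unscheduled ECGs and those taken at withdrawal (9.3.7) and safety follow-up (9.3.8). This stands.

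**Conclusion.** The gap is real and modest. Any Class 1A or Class 3 agent that the CYP3A4 and P-gp items do not catch may be started on treatment with the investigator's agreement. No rule is triggered by the drug, and no ECG is tied to it. After Week 5 the next scheduled Part B ECG can be up to 140 to 168 nominal days away, assuming that no unscheduled, withdrawal or follow-up ECG comes first. Need should be uncommon, since criteria 12c, 17, 18 and 20 remove most cardiac risk at entry.

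Two stronger readings are not supported.

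- A reader might conclude that the use would certainly go uncounted in the SAP's deviation tables. SAP 2.1.6.1 has a category for excluded medication but does not define it, and the separate data handling rules are not among the documents. What can be said is that nothing in the protocol makes the use a deviation; it would be recorded as a concomitant medication.
- A reader might also infer biased QTcF summaries, altered Part A DLT decisions or an added QT effect. The documents give no rate of use and no QT effect for these drugs. Protocol 4.1.2.5 describes the QTc changes in the overseas phase 1 study as independent of drug administration, and the thorough QTc results are redacted. No msec effect, case count or effect on results is claimed.

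**What to change.** Add Class 1A and Class 3 antiarrhythmics to the list in 7.3.1. Add one sentence: if such a drug becomes medically necessary, record the deviation, decide case by case whether TAK-385 continues, and take a 12-lead ECG at or before the next visit under the existing additional-assessment notes in Appendices A, B and C. Withdrawal under 7.5, item 2, would apply only where the risk is judged unacceptable; there should be no automatic stop.

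The list line alone brings no ECG forward. The added sentence does that, and only if the investigator orders the ECG.

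The cost is one line and one sentence at the next amendment, with no new SAP output. The downside is an occasional extra deviation or discontinuation, and Part B withdrawals are not replaced.
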